### **Analytical Plans**

All final analyses will be conducted using SAS 9.3; R cmprsk will be used for the competing risk analyses.

- **Baseline Characteristics by Treatment**

The adequacy of randomization is assessed by comparing the distribution of baseline characteristics among the treatment groups: demographics (age, gender, marital status, ethnicity, race, education); physical and medical history measures (weight, BMI, waist/hip ratio, abdominal obesity, systolic and diastolic blood pressure, edema, type of index event (stroke, TIA), presence of carotid angioplasty and carotid endarterectomy before randomization, prior stroke before index event, MI, history of hypertension, history of CHF, atrial fibrillation,

coronary angioplasty, CABG, smoking status, history of coronary artery disease (CABG, angioplasty, or hospitalization for MI) modified MMSE score, NIH stroke scale score, modified Rankin grade; symptoms and complaints (headaches, muscle aches, sinusitis, pharyngitis, teeth problems, shortness of breath); laboratory values (HOMA, glucose, ALT, A1C, hemoglobin); prescription and non-prescription medications (aspirin, multivitamin, anti-hypertensives, loop diuretics, lipid lowering agents, anti-arrhythmic drugs, anti-coagulants, anti-platelets, other). Continuous variables will be examined for skewness, outliers, or other departures from a normal distribution graphically (side-by-side histograms, boxplots, normal quantile plots) and by side-by-side summary statistics (means, standard deviations, medians, quartiles, etc.). Inferences on differences in the means for continuous variables (e.g. age, BMI, weight) by treatment groups are accomplished through two-sample t tests. F tests for equality of variances are used to identify the appropriate statistical tests for continuous measures.

Categorical variables are examined by calculating frequency distributions. The chi-square test or Fisher's exact test (when cell counts are less than 5) are used for comparing the distribution between treatment groups. Except for medical history questions, analyses are run with "Unknown", "Uncertain", and "Refused" responses coded as missing and "Missing" excluded from the analysis. For the following medical history variables, the analyses are run with "Unknown" and "Refused" coded as missing (excluded from the analysis) and "Uncertain" responses counted as 'no' or 'absent' responses: Prior stroke before index event, MI, history of hypertension, history of CHF, coronary angioplasty, CABG, smoking status, symptoms and complaints (headaches, muscle aches, sinusitis, pharyngitis, teeth problems, shortness of breath).

- *Analysis of Primary Outcome*

All analyses will be by intention-to-treat. That is, participants will be analyzed according to their original treatment assignment, regardless of adherence. The analysis will not be adjusted for site because of the large number of sites and the few numbers of participants enrolled at many of the sites. The analysis of the primary endpoint, time to first stroke or MI, will be tested by the log rank statistic, with an experiment-wide type I error of 0.05 (2-sided) as the level of significance. Cumulative event-free rates for the primary endpoint, as well as the individual components (stroke and MI), will be calculated using the method of Kaplan-Meier. Cox proportional hazards models will be used to examine the effect of treatment. The proportional hazards assumption will be tested by treatment by time interaction term. Breslow's approximation, which is the default in PROC PHREG in SAS, will be used to handle tied event times when ties are relatively few. If data are heavily tied we will use Efron's method, which gives closer results to the exact results than Breslow's approximation. The treatment effect will be summarized as a hazard ratio (pioglitazone vs. placebo) with 95% confidence interval adjusted for the interim looks.

Because of the size of this study, we expect that the randomization process will produce comparable groups of participants and balance. However, in a secondary sensitivity analysis, we will adjust for the following pre-specified set of baseline variables that may affect prognosis or treatment effect: age, gender, systolic blood pressure, diastolic blood pressure, history of hypertension, type of entry event (i.e., TIA or ischemic stroke), history of prior stroke before the index event, history of coronary artery disease (history of CABG, angioplasty, or hospitalization for MI), and current smoking. In addition, secondary analyses of the effect of treatment in predefined baseline subgroups will be examined by tests of interaction adjusted for multiplicity. The pre-specified subgroups are:

- Age in years
- Gender
- Race (defined as white, black and other)
- Ethnicity (Hispanic vs. non-Hispanic)
- HDL cholesterol
- Fasting plasma glucose
- HOMA
- HbA1c
- Triglyceride
- BMI
- History of hypertension
- History of coronary artery disease (CABG, Angioplasty, or hospitalization for MI)
- Medication adherence (percent of mgs taken based on protocol dosage)
- Medication adherence (<80% vs. ≥80% of mgs taken based on protocol dosage).

Cox proportional hazards models will be used to examine the effect of treatment in these adjusted and subgroup analyses. The Hochberg procedure, a sequentially rejective variation of the Bonferroni procedure, will be used to determine significance using an overall type I error of 0.05 (two-sided). Subgroups analyzed as a continuous measure that are determined to significantly interact with treatment will be further explored based on established clinical cutpoints.

Additional subgroup analyses that will be considered for exploratory tertiary analyses are baseline CRP, baseline statin use, change in HOMA from baseline to year 1, change in CRP from baseline to year 1, change in HbA1c, baseline triglyceride/HDL ratio, baseline non-HDL cholesterol (total cholesterol-HDL cholesterol), atrial fibrillation, and subtype and territory of index event.

- *Analysis of Secondary Outcomes: Stroke, ACS, All-Cause Mortality, Stroke, MI or serious CHF, Diabetes*

Any stroke, acute coronary syndrome, all-cause mortality, stroke, MI or serious CHF, and progression to diabetes will be analyzed as time to first event in the same manner as the primary endpoint principal analysis. The treatment effect will be summarized as a hazard ratio (pioglitazone vs. placebo) with 95% confidence interval. To provide some control for multiplicity of secondary outcomes, the Hochberg procedure will be used to determine significance using an overall type I error of 0.05 (two-sided).

- Sensitivity Analyses

In addition, depending on the availability of resources, several sensitivity analyses of IRIS outcomes may be conducted using updated criteria that have evolved since initiation of the study (see Appendix 1):

- (1) Analysis of the effect of treatment on risk of the primary outcome (stroke or MI) using adjudicated MI outcomes based on the 2012 ESC/ACCF/AHA/WHF criteria for MI and the 2013 AHA/ASA criteria for stroke.
- (2) Analysis of the effect of treatment on risk of stroke using adjudicated stroke outcomes based on the 2013 AHA/ASA criteria.
- (3) Analysis of the effect of treatment on risk of ACS using adjudicated MI outcomes based on the 2012 ESC/ACCF/AHA/WHF criteria for MI.
- (4) Analysis of the effect on treatment on risk of the composite safety outcome (stroke, MI, serious CHF) with new MI based on the 2012 ESC/ACCF/AHA/WHF criteria and new stroke criteria based on the 2013 AHA/ASA criteria.
- (5) Analysis of the effect of treatment on progression to diabetes using adjudicated diabetes outcomes based on the revised 2010 ADA criteria for diabetes.

- Competing Risks Sensitivity Analysis

The occurrence of individual secondary outcomes (stroke, ACS, stroke, MI or serious CHF, and diabetes) may be circumvented by death. Naively censoring patients who fail from all-cause mortality in analyzing time to first occurrence of any of these secondary outcomes could lead to biased estimates. The Cox model commonly used in classical survival analysis is a valid analysis for cause-specific hazard in the presence of competing risks. But if we are interested in the cause-specific cumulative incidence, the Gray and Fine & Gray methods are more appropriate.

A competing risks sensitivity analysis will be conducted using these two methods. More specifically, Gray's test for subdistribution hazards will be used for comparing the cumulative incidences of each secondary outcome by treatment group and the proportional subdistribution hazards model proposed by Fine & Gray will be used to estimate the treatment effects (subdistribution hazard

ratios). The methodologies described above are available in and will be implemented through the R *cmprsk* package.

Gray's test will be compared with the logrank test for the treatment effect. We will also compare the subdistribution hazard from Fine-Gray model to the cause specific hazard from the Cox model to improve understanding of the treatment effect. A cumulative incidence curve will be compared to Kaplan-Meier curve.

- *Analysis of Secondary Outcomes: Cognitive Decline (Modified MMSE Score)*

To determine whether pioglitazone, compared to placebo, reduces the risk for cognitive decline, as measured by the modified MMSE score, a longitudinal analysis will be done. Repeated measures of the modified mini mental state exam will be analyzed by mixed model methods adjusted for the study design. In addition, secondary analyses will be conducted comparing participants who decline from a normal modified MMSE score ( $\geq 90$ ) to an exit score of  $< 78$  by treatment groups using a logistic model.

The primary analysis will be based on an analysis of covariance mixed model approach using maximum likelihood estimation assuming missing data are missing at random. All participants with available data will be included in the model. Initially, we will determine the most appropriate covariance structure for the repeated outcomes and then fit the mean model. Treatment by time interactions will be examined to determine whether the treatment effect is constant over time. If there is evidence of an interaction ( $p < 0.05$ ), the data will be analyzed by time point.

- *Sensitivity Analysis for Cognitive Data*

The mixed effects model based on maximum likelihood estimation is unbiased if missing data are unrelated to outcomes, i.e., if the data are considered missing at random (MAR) or missing completely at random (MCAR). Nevertheless, because it is not always known whether missing data are ignorable and because missing observations have the potential to alter the results of analyses, the pattern of missing data and dropouts will be examined among the two treatment arms. We will also examine whether the outcome is related to missingness by using logistic regression models to determine if the outcome measure at the follow-up time preceding the missed visit predicts the missing value and if baseline value predicts non-intermittent missing (i.e., missing last expected score). If there are no systematic differences between those with and without missing data, the data can be considered to be observed (and missed) at random. If the outcome measure is predictive of missing data, it would indicate that the missing data are potentially not MAR or MCAR. Also, if there are no covariates predictive of missing data it would be another indication that the data may likely be MAR. If the missing data are determined to be possibly non-ignorable and there is a reasonable likelihood that the conclusions could be altered by the missing information, sensitivity

analyses will be considered to determine the impact of missing information on the treatment comparisons including the approach proposed by Carpenter et al. (e.g., multiple imputation that reflects the behavior of the missing data or including variables that are predictive of missingness in the model).

SAS code for all completed analyses is available upon request.

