### Study Design

The Insulin Resistance Intervention after Stroke Trial (IRIS) is a double-blind, placebo-controlled, multi-center clinical trial in which approximately 4000 non-diabetic patients  $\geq 40$  years of age with insulin resistance and a recent non-disabling ischemic stroke or TIA are randomly assigned to pioglitazone, a thiazolidinedione (TZD), or placebo. Randomization is stratified by participating site using a random permuted block design of varying block size (4, 6, 8) and treatment allocation ratio of 1:1 between placebo and active drug. Maximum follow-up will be 5 years (plus 21 days allowed after the 5 year anniversary to complete the exit interview) and the average follow-up duration will be approximately four years. Participants who experience a stroke or MI during follow-up will be maintained on their randomized study drug and will continue to be followed for the occurrence of other primary and secondary outcomes until they are withdrawn at trial termination or are censored due to death.

To rigorously evaluate the effect of treatment on each defined secondary outcome, the strategy of retaining participants on treatment after a primary endpoint is considered as a requirement. A participant who experiences an MI at day 60 after randomization and a subsequent stroke at day 300 will be analyzed as an outcome for the primary analysis at day 60 (time to first stroke or MI). However, for the analysis of stroke alone, a participant will be counted as event free until day 300 (time to first stroke). This design allows for the detection of an effect of treatment

on stroke regardless of the treatment effect on the occurrence of MI. Similar contingencies pertain for the other secondary outcomes.

The occurrence of initial vascular events may affect a participant's ability and willingness to continue on his or her assigned study drug. Although all analyses will be conducted according to the intention-to-treat principle, an early effect of treatment on one type of outcome (e.g., stroke) may systematically alter compliance by treatment group, thus affecting the ability to detect an effect of treatment on later events. Because of this concern, every effort will be made to maintain each participant on his or her assigned treatment, both before and following any vascular event they may experience.

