The adequacy of randomization is assessed by comparing the distribution of baseline characteristics among the treatment groups: demographics, physical and medical history measures, symptoms and complaints, prescription and non-prescription medications. Continuous variables are examined for skewness, outliers, or other departures from a normal distribution graphically and by summary statistics. F tests for equality of variances are used to determine the appropriate statistical test for continuous measures. Categorical variables are examined by calculating frequency distributions.

- Protocol adherence

Protocol adherence is monitored monthly by the Operations Committee to assure early identification of poor performance at individual sites and in the trial overall. Periodic reports are provided to the DSMB and whenever requested. Specific parameters to be monitored include:

- Randomization of ineligible participants
- Treatment allocation errors (participant put on wrong treatment)
- Failure to obtain required blood tests on time
- Failure to complete required follow-up interviews on time
- Loss and withdrawal rates
- Treatment adherence (pill counts, cessation of use)
- Failure to complete endpoint adjudication on time (within 30 days)
- Use of TZDs outside of trial protocol
- Continued use of trial medication despite contra-indication (e.g., hemoglobin <8.5 g/dl, ALT >2.5x upper limit of normal)

- Monitoring for Efficacy

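### Study-drug adherence, measured after randomisation, is listed twice among the baseline subgroups, so two of the 14 multiplicity-controlled secondary interaction tests do not compare randomised groups and are open to bias

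*SAP*

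**What the plan says.** Under Analysis of Primary Outcome, the SAP states that "secondary analyses of the effect of treatment in predefined baseline subgroups will be examined by tests of interaction adjusted for multiplicity". A list of 14 items follows. Twelve are demographic, laboratory or medical-history variables. The last two are "Medication adherence (percent of mgs taken based on protocol dosage") and "Medication adherence (<80% vs. ≥80% of mgs taken based on protocol dosage").

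Cox models are to be used, and the Hochberg procedure "will be used to determine significance using an overall type I error of 0.05 (two-sided"). A separate, lower tier follows: "Additional subgroup analyses that will be considered for exploratory tertiary analyses are baseline CRP", and so on. Adherence is not in that lower tier.

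Two other sections bear on what adherence is. Interim Monitoring Plan, under Protocol adherence, lists it among the things watched while the trial runs: "Treatment adherence (pill counts, cessation of use"). Study Design warns that "an early effect of treatment on one type of outcome (e.g., stroke) may systematically alter compliance by treatment group", and also that a first vascular event may make a participant less able or willing to stay on study drug.

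**The concern.** A subgroup interaction test has a causal reading because randomisation balances the arms within each level of a variable fixed before treatment. Adherence is not fixed before treatment. Assigned drug, tolerability, prognosis and the outcome itself can all influence it. Participants below 80% on pioglitazone may differ in prognosis from those below 80% on placebo, and likewise above 80%. The within-stratum hazard ratio then mixes any drug effect with the difference between the people compared.

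The stake is how a result would be read. An adherence interaction that passed the Hochberg step would carry the standing of a pre-specified, multiplicity-controlled baseline subgroup finding. Hochberg limits chance rejections across a family of valid tests; it does nothing for a test whose null distribution is shifted by selection. Coding the same variable twice also spends two steps of a procedure shared with the 12 genuine baseline variables.

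**Working it through.** **No plan figure to reproduce.** The SAP gives no adherence rate and no operating characteristic for the subgroup tests. The check is a count, a comparison of sections and a simulation.

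**Count and thresholds.** The list has 14 items, 2 of them adherence. The strictest Hochberg step is 0.05/14 = 0.00357. With 12 items it is 0.05/12 = 0.00417.

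**Sections side by side.** The list is introduced as baseline. Protocol adherence describes adherence as pill counts and cessation, which exist only during follow-up. Study Design says treatment and events can move compliance. The label and the variable do not agree.

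**Simulation inputs from the SAP.** N = 4000, 1:1; four-year risk 27% on placebo and 22% on pioglitazone; average follow-up about 4 years.
- Placebo hazard: −ln(1 − 0.27)/4 = 0.0787 per year.
- Design hazard ratio: ln(0.78)/ln(0.73) = 0.789.

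**Assumed inputs (not in the SAP).** Follow-up uniform over 3–5 years; prognosis u standard normal with log hazard ratio 0.6 per SD; non-adherence from

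logit P(adherence <80%) = −0.85 + g·u + s·(pioglitazone) + e·(event),

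where g may differ by arm. This gives about 30–38% non-adherent on placebo and 30–48% on pioglitazone. The treatment hazard ratio is the same for every patient, so no effect modification is built in.

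**Test.** Z = [ln RR(non-adherent) − ln RR(adherent)] / √(sum of 1/events over the four cells), with 1000 runs per scenario. Monte Carlo error at 5% is √(0.05 × 0.95/1000) = 0.7 percentage points.

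Rejection rates are shown for true HR 1.0 / true HR 0.789. Apparent HRs are for true HR 1.0.

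| Scenario | g placebo, g pioglitazone, s, e | Reject at 0.05 (%) | Reject at 0.05/14 (%) | HR adherent; non-adherent |
|---|---|---|---|---|
| Adherence unrelated to anything | 0, 0, 0, 0 | 5.3 / 4.9 | 0.4 / 0.4 | 0.997; 0.995 |
| Same link to prognosis | 0.4, 0.4, 0, 0 | 5.4 / 4.8 | 0.1 / 0.6 | 1.000; 0.996 |
| Same link, more non-adherence on drug | 0.4, 0.4, 0.5, 0 | 5.4 / 5.2 | 0.5 / 0.2 | 0.971; 0.975 |
| As above, events also reduce adherence | 0.4, 0.4, 0.5, 1 | 4.6 / 6.1 | 0.3 / 0.4 | 0.869; 0.895 |
| Reasons differ by arm, mild | 0.4, 0.2, 0.5, 0 | 13.5 / 11.3 | 1.6 / 1.4 | 1.027; 0.919 |
| Reasons differ, moderate | 0.4, 0, 0.5, 0 | 41.7 / 38.2 | 12.0 / 9.4 | 1.078; 0.861 |
| Reasons differ, strong | 0.8, 0, 0.5, 0 | 88.0 / 84.9 | 58.7 / 56.0 | 1.152; 0.771 |
| Strong, events also reduce adherence | 0.8, 0, 0.5, 1 | 58.5 / 46.2 | 23.3 / 14.5 | 1.070; 0.805 |

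The nominal rate at 0.05/14 is 0.36%.

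**Reading the table.** In the first four rows the interaction test keeps its level. In the fourth, however, both subgroup hazard ratios fall below 0.90 although the drug does nothing, so a sound test level does not make the subgroup estimates sound. In the last four rows the test itself is inflated.

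**The case against.** The strongest reply is that little hangs on these two items. The SAP calls them secondary, the primary test is an intention-to-treat log-rank analysis, and no event target, stopping boundary or primary or secondary endpoint analysis uses adherence. That stands. A reader might infer that the tests are confirmatory or that the main result is compromised; the SAP supports neither.

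A reader might also infer that the tests are certainly biased. They are not: the interaction test is inflated only when the reasons for non-adherence differ by arm. Study Design makes a dependence of adherence on treatment and events plausible, but its stated worry is compliance after a first event and its consequence for later events. It does not describe the arm-specific mechanism in the inflated rows. Those rates are illustrations, and quoting the 0.05 figures alone would ignore the stricter Hochberg step.

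Nor should one assume the bias would flatter adherers. In the inflated rows with no drug effect, the apparent benefit lies in the non-adherent.

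The multiplicity cost to the other 12 tests is slight and in the conservative direction.

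Finally, the lower tier also contains post-randomisation variables, "change in HOMA from baseline to year 1, change in CRP from baseline to year 1" among them. One might extend the criticism to these, but the SAP already labels them exploratory tertiary and only says they will be considered.

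What remains is the mislabelling and the placement. Calling the analysis secondary does not make adherence a baseline variable, and the formal Hochberg family ranks it above the exploratory tier.

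**Conclusion.** The point holds as a flaw of classification and placement in a secondary analysis, worth correcting but not critical to the trial's main conclusion. Two of the 14 listed interaction tests, and the hazard ratios reported with them, are not protected by randomisation.

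The SAP cannot settle the size. Under the assumed mechanisms, false rejection runs from nominal to roughly eight times nominal at 0.05 in the moderate case (41.7/5 = 8.3). At 0.05/14 the moderate case gives 9–12% against 0.36%. The strong rows show that more extreme assumptions give more, but nothing in the SAP indicates that they apply.

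Two limits apply. The simulation covers only the 80% split, with a rate-ratio test standing in for the Cox interaction term; the continuous version was not simulated. The 0.05/14 figures are also a floor for Hochberg rejection, because later steps are looser when larger p-values also pass.

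**What to change.** Delete both adherence items from the predefined baseline subgroup list and from the Hochberg family, leaving 12 baseline tests with a strictest step of 0.0042 instead of 0.0036.

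If adherence is still to be examined, put it in a separate paragraph, labelled exploratory and non-randomised, with a method suited to a post-randomisation variable and its assumptions written out. One example is a complier-average causal effect with randomisation as the instrument. It needs a definition of complier and the assumption that assignment acts on outcome only through drug taken. Inverse-probability-of-censoring weighting at discontinuation is another possibility, but it should not be presented as resting on randomisation alone, because it also assumes no unmeasured common predictors of discontinuation and outcome.

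The cost is a short SAP wording change and minor programming. It requires no new data, and the SAP's date (3/1/2015) precedes the exit-interview window it gives (March 9 to July 7, 2015).

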#### **Primary Objective**

1. To determine if pioglitazone, compared to placebo, will reduce the overall risk for fatal or non-fatal stroke or fatal or non-fatal MI among non-diabetic men and women 40 years or older with insulin resistance and a recent ischemic stroke or TIA.

Among non-diabetics with insulin resistance, we hypothesize that pioglitazone will reduce the occurrence of any primary endpoint (fatal or non-fatal stroke or MI) within four years from 27% to 22%.

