Three interim “looks” at the primary endpoint data for treatment efficacy are planned. The proposed stopping boundaries for the interim analyses are based on the work of Lan and DeMets and of Wang and Tsiatis and are calculated using East Version 4. Since it is unlikely that there will be an adequate number of events during the first year to evaluate efficacy, interim “looks” are proposed after 227 events (one-fourth of total events), 454 events and 681 events are observed in the trial cohort, with the final analysis at 908 events, the total number of events selected for the trial. The stopping boundaries are designed to be flexible; therefore, the actual timing of the analyses will be based on Data and Safety Monitoring Board request. The Data and Safety Monitoring Board will review all interim analyses. If the interim analyses indicate a significant treatment effect or a very low conditional probability of detecting the estimated treatment effect (see Figure 1), the DSMB may choose to stop the trial prematurely.

- Monitoring for Futility

A futility analysis for the primary endpoint is planned during the 2nd and 3rd interim analyses (see Figure 1), which will occur after approximately 454 events of stroke or MI events have been observed and after 681 events. If either of these analyses shows that the nominal critical point (Z-score) for the primary endpoint crosses the internal boundary for futility, it would indicate that the observed effect size is much smaller than anticipated and that the trial has very low conditional power to detect the estimated treatment effect for the primary outcome. In addition to these futility analyses, the observed primary outcome event rate and rate of information accrual (number of events) is monitored from the initiation of the trial and compared with the expected rates. Based on these rates an estimated time for study completion (i.e. time to reach 908 events) and the estimated number of events that will be reached by the scheduled end of the trial is presented to the DSMB. When considering the futility analyses and rate of information accrual, the DSMB may also consider other internal evidence of futility (i.e., secondary outcomes) and has the option of recommending early termination of the trial or continuing with a possible adjustment to sample size.

[figure not shown]

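### The competing-risks sensitivity analysis omits the primary stroke/MI composite and the MI component, so their absolute risks rest on Kaplan-Meier alone (minor; hazard ratio and test unaffected)

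*SAP*

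**What the plan says.** The SAP's *Study Outcomes* section defines the primary outcome as time to first stroke or MI, fatal or non-fatal. A death from any other cause is not an event.

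Under *Analysis of Primary Outcome*, the comparison is a log-rank test "with an experiment-wide type I error of 0.05 (2-sided) as the level of significance", and the effect is summarised as a Cox hazard ratio with a confidence interval. For absolute rates, "Cumulative event-free rates for the primary endpoint, as well as the individual components (stroke and MI), will be calculated using the method of Kaplan-Meier". No other estimator of absolute risk is given for the primary endpoint.

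Under *Competing Risks Sensitivity Analysis*, the SAP reasons that "The occurrence of individual secondary outcomes (stroke, ACS, stroke, MI or serious CHF, and diabetes) may be circumvented by death". It warns that simply censoring deaths may bias estimates. It accepts the Cox model for the cause-specific hazard and prefers the Gray and Fine-Gray methods for cumulative incidence. Gray's test is then assigned to "comparing the cumulative incidences of each secondary outcome by treatment group". The planned comparison of cumulative incidence curves with Kaplan-Meier curves belongs to that same secondary-outcome analysis.

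**The concern.** The SAP's reason for a competing-risks analysis is that death can prevent the event of interest. That reason applies fully to the primary composite, because a participant who dies of cancer, for example, can no longer have a first stroke or MI. It applies also to MI alone, for which Kaplan-Meier rates are planned and for which even a fatal stroke is a competing event. The SAP gives no reason for leaving these two out.

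What is at stake is absolute risk. One minus Kaplan-Meier, with other-cause deaths censored, estimates risk in a hypothetical setting without those deaths. It exceeds the cumulative incidence whenever such deaths occur. The *Primary Objective* is worded as a four-year risk falling from 27% to 22%, so readers will look for absolute risks on this endpoint, and the plan supplies only the estimator that runs high.

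**Working it through.** **Inputs from the SAP.** Four-year primary-event risk 27% on placebo and 22% on pioglitazone (*Primary Objective*); "approximately 4000 non-diabetic patients" with a "treatment allocation ratio of 1:1 between placebo and active drug" (*Study Design*); "with the final analysis at 908 events, the total number of events selected for the trial" (*Monitoring for Efficacy*).

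**Assumptions.** The SAP gives no rate of death from other causes, so a range is used. Its background figure of 6% dying of stroke or MI within five years cannot serve, because those deaths are primary events. The SAP does not say whether 27% and 22% are Kaplan-Meier or cumulative-incidence risks; they are taken here as one minus Kaplan-Meier. Hazards are taken as constant.

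**Step 1: the plan's own event figure.** The implied hazard ratio is ln(0.78)/ln(0.73) = 0.789. Schoenfeld's formula then needs 562, 753 or 931 events for 80%, 90% or 95% power at two-sided 0.05. With 908 events the power is 94.5%, before any allowance for interim looks or non-adherence. The SAP states no power, so 908 can be neither confirmed nor refuted. At the hypothesised risks, 4000 patients give 2000 × (0.27 + 0.22) = 980 events in four years. None of this depends on how absolute risk is estimated.

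**Step 2: event hazards.** From 1 − exp(−4λ):
- placebo: λ = −ln(0.73)/4 = 0.0787 per year
- pioglitazone: λ = −ln(0.78)/4 = 0.0621 per year

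**Step 3: cumulative incidence with other-cause death hazard μ, equal in both arms.** CIF(4) = λ/(λ+μ) × [1 − exp(−4(λ+μ))].

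For example, placebo with μ = 0.03: 0.0787/0.1087 × (1 − 0.73 × exp(−0.12)) = 0.724 × 0.3525 = 25.5%.

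| Assumed μ per year | Placebo | Pioglitazone | Difference (points) | Excess of 1−KM, placebo / pioglitazone (points) |
|---|---|---|---|---|
| 0 (1−KM) | 27.0% | 22.0% | 5.0 | – |
| 0.01 | 26.5% | 21.6% | 4.9 | 0.5 / 0.4 |
| 0.02 | 26.0% | 21.2% | 4.8 | 1.0 / 0.8 |
| 0.03 | 25.5% | 20.8% | 4.7 | 1.5 / 1.2 |

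A wider range, 2% to 15% other-cause death over four years, gives 26.7%/21.8% down to 25.0%/20.4%. The excess is then 0.2 to 2.0 points per arm. The risk ratio hardly moves (0.815 by Kaplan-Meier, 0.814-0.815 by cumulative incidence).

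**Step 4: unequal other-cause mortality.** With four-year other-cause death of 6% on placebo:
- 4% on pioglitazone: the cumulative-incidence difference is 4.65 points, so Kaplan-Meier (5.00) overstates it.
- 8% on pioglitazone: the difference is 5.08 points, so Kaplan-Meier understates it.

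Solving for a difference of exactly 5.00 gives a break-even other-cause death hazard on pioglitazone of about 1.22 times that on placebo. This factor is stable for placebo other-cause death between 4% and 12%.

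**The case against.** The strongest reply is that the plan's inference on the primary endpoint is sound as it stands. The log-rank test and Cox model address the cause-specific hazard, and the SAP itself says that the Cox model is valid for that purpose under competing risks. This stands in full.

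A second reply is that much of the ground is already covered. Stroke alone is in the competing-risks analysis, MI is contained in ACS, and the stroke/MI/serious CHF composite contains every primary event. A reader will see there how far the two curves diverge. MI alone is not one of the six secondary outcomes, so its absence from a section on secondary outcomes is not a contradiction. This limits the gap but does not close it: the numbers for the primary endpoint itself would still come from Kaplan-Meier only.

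Two stronger readings are tempting, and the SAP does not support them.

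- A reader might infer that the trial's headline risk difference or number needed to treat will be overstated. The SAP specifies neither; its effect measure is the hazard ratio. If someone derives a difference from the Kaplan-Meier rates, the direction of its error depends on other-cause mortality by arm (Step 4). Nor can a Kaplan-Meier estimate be called too large against the 27% and 22%, since the SAP does not say which kind of risk those are.
- A reader might infer that a treatment effect on other deaths would go unnoticed. All-cause mortality is a separate time-to-event secondary outcome and is also monitored for safety.

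**Conclusion.** The omission is real and does not follow the SAP's own reasoning. Its effect is confined to absolute risks for the primary composite and for MI. For the composite, one minus Kaplan-Meier overstates each arm's real-world four-year risk by about 0.4-1.5 points. That rests on constant hazards, on 27% and 22% being Kaplan-Meier risks, and on an assumed other-cause death rate of 1-3% per year, equal in both arms. Upward error in each arm's risk is certain once other-cause deaths occur; only its size is assumed. A derived difference would move by a few tenths of a point at most in the scenarios tried, in either direction. No size is computed for MI alone, because the SAP gives no MI-specific hypothesis.

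The primary test, the hazard ratio and the event target do not change. Severity is minor: this is a cheap improvement.

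**What to change.** Extend *Competing Risks Sensitivity Analysis* to two further endpoints:

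- the primary composite, with death not due to stroke or MI as the competing event;
- MI, with non-MI death as the competing event.

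For both, run Gray's test and the Fine-Gray model and show cumulative incidence curves beside the Kaplan-Meier curves. Take any absolute risk reported for these endpoints from the cumulative incidence function, with confidence intervals. Keep the log-rank test and Cox hazard ratio as the primary analysis; the additions are sensitivity analyses and make no claim on the type I error.

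The cost is a few more calls to the R cmprsk package that the SAP already names, and slightly lower quoted absolute risks. Adding this before the results are known also avoids a later choice of estimator for the main endpoint.
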